#### **Scientific objectives**

The objective of this study is to evaluate the performance of a miniaturized sleep apnea test, called NightOwl. The system consists of a sensor placed on the fingertip and a cloud-based analytics software. The sensor acquires accelerometer and photoplethysmographic data. The software derives actigraphy from the former, and blood oxygen saturation and peripheral arterial tone (PAT), among other features, from the latter. In order to assess NightOwl's performance, we will compare the respiratory event index (REI), defined as the number of respiratory events per hour of sleep, derived by the NightOwl system, to the AHI obtained from manual analysis of the polysomnography (PSG), which is the gold standard for sleep apnea diagnosis. We will also compare the total sleep time (TST) derived by both systems. This study will be performed in a sleep lab environment.

As of March 2017, the new clinical practice guideline for diagnostic testing for adult sleep apnea of the American Academy of Sleep Medicine (AASM) for the first time formulates a strong recommendation that both polysomnography (PSG) and home sleep apnea testing (HSAT) are appropriate diagnostic testing options for uncomplicated adult patients who are at increased risk of moderate to severe sleep apnea.

Collop et al. performed a comprehensive analysis of the evidence for HSAT devices to diagnose obstructive sleep apnea (OSA) in out-of-center settings. The authors concluded that testing devices that analyze changes in peripheral arterial tone (PAT) in combination with actigraphy and blood oxygen saturation (SpO2) are adequate to diagnose OSA in patient populations with a high pre-test probability.

In this study, we wish to assess the performance of a system for the diagnosis of OSA that measures and analyzes the abovementioned parameters, called NightOwl. The system consists of a small sensor device which is placed on the fingertip and a cloud-based analytics platform. An illustration of the NightOwl sensor can be found in Figure 1.

**Figure 1: A photograph of the NightOwl sensor positioned on the index finger (source: <https://www.resmed.com.au/sleep-apnea/sleep-study>)**

It is designed to be self-applied and initiated by the patient by attaching the sensor to the fingertip by means of an adhesive patch.

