**Figure 2 - Flowchart of study. Experimental signifies procedures that are performed exclusively for research purposes.**

#### Frequency and duration

We aim to include between 10 and 19 subjects every study night. Each patient has one night of recording.

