#### Sample collection

Data of the PSG and NightOwl will be collected throughout the entire duration of the overnight PSG study.

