**Table 1: Self-reported options for Ethnicity and Race**

The NightOwl sensor will be attached to the middle finger of the hand on which the pulse oximeter of the PSG is applied by means of a disposable adhesive fingerwrap. The NightOwl sensor will be switched on and connected to a smartphone on which the NightOwl Companion App is installed. The NightOwl Companion App continuously acquires the raw sensor data from the NightOwl Sensor and stores this data on its internal memory. After starting the acquisition of the NightOwl sensor data via the NightOwl Companion App, the PSG recording can be started.

When the personnel press the ‘Wake up’ button in the NightOwl Companion App at the end of the PSG study, the data will be uploaded to a secure cloud server in which the raw NightOwl Sensor data is stored and on which the NightOwl Software, which analyses the data, is deployed.

After pressing the ‘Wake up’ button in the NightOwl Companion App, the PSG equipment and NightOwl sensor will be detached from the subject. The NightOwl Sensor will be disinfected and cleaned. The following disinfectants can be used on the sensor:

- Mikrozid
- Clorox
- Lysol
- Cavicide
- 70% Ethyl alcohol or isopropyl alcohol (IPA)

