#### Potential Risk and protection against such risk

A non-serious risk for cytotoxicity or skin irritation caused by the sensor material being in continuous contact with the fingertip for the overnight recording could be identified. However, this risk is deemed negligible since the sensor enclosure material passed ISO10993-1 compliant tests for cytotoxicity and Direct Primary Skin Irritation.

A risk for discomfort of the subject caused by the tight application of the NightOwl sensor to the finger exists. In order to mitigate this risk, the subject will be explicitly encouraged to either contact the clinical personnel to reapply the sensor more loosely or to detach the sensor from the finger.

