#### Study analysis

Two main performance analyses will be performed:

- The evaluation of the Pearson correlation between the REI and TST estimate obtained from the NightOwl and the AHI and TST determined from the PSG;
- The evaluation of the agreement between patient categorization (into sleep apnea severity categories) obtained by the NightOwl and those obtained by the manual analysis of the PSG.

In order to establish an external benchmark to which the NightOwl and PSG analysis could be compared, the codified PSG data will be transferred to Younes Medical Technologies Ltd. (YMT), the corporation behind the Michele Sleep Scoring System (MSSS) developed by [name]. Malhotra et al. confirmed that the MSSS, complemented with manual editing, standardizes PSG scoring results within and across sleep centers. Using such external benchmark, the impact of inter-scorer variability of current and future reports on NightOwl's performance metrics is reduced.

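### Total sleep time is compared only by correlating minutes from a recording window both systems share, so varying night length could by itself produce a positive correlation

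*Combined protocol and SAP*

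**What the plan says.** Scientific objectives names TST as a comparison: "We will also compare the total sleep time (TST) derived by both systems". It also makes sleep time the denominator of the respiratory event index (REI). Study analysis says how TST is assessed: the "Pearson correlation between the REI and TST estimate obtained from the NightOwl and the AHI and TST determined from the PSG". The agreement analysis in that section covers apnea severity categories only. For TST there is no mean difference, limits of agreement, sleep efficiency comparison, epoch-level sleep/wake comparison or adjustment for recording time. The section sets no null value, alpha or success threshold for r.

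The recording window is shared by design:

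- Sample collection: "Data of the PSG and NightOwl will be collected throughout the entire duration of the overnight PSG study".
- Start (detailed nightly procedure, text after Table 1): "After starting the acquisition of the NightOwl sensor data via the NightOwl Companion App, the PSG recording can be started".
- End (same text): staff press the wake-up "button in the NightOwl Companion App at the end of the PSG study".
- Frequency and duration: "Each patient has one night of recording".

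There is one exception. Under the potential risks, an uncomfortable subject is encouraged to "contact the clinical personnel to reapply the sensor more loosely or to detach the sensor from the finger", so some NightOwl windows may be shorter than the PSG window.

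**The concern.** A subject's TST is the length of the recording multiplied by the fraction of it scored as sleep. NightOwl's contribution is the fraction; the length is set by when staff start and stop both systems. If nights differ in length between subjects, the two TST values rise and fall together whether or not NightOwl's sleep/wake scoring carries information.

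This is a different matter from the familiar one that Pearson's r ignores an offset or a scale error. Here r itself is partly made by a quantity that the device does not have to estimate. A positive TST correlation could then be taken as evidence that the actigraphy detects sleep when part of it comes from the schedule. Since sleep time is also the REI denominator, that reading would matter beyond TST.

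**Working it through.** The protocol states no target correlation, power or variance, and 100 subjects is given without derivation, so there is no figure of its own to reproduce.

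**Inputs from the protocol.** Shared recording window, one night per subject, n = 100, Pearson r on TST minutes.

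**Assumptions, not in the protocol.** Recording length T has mean 420 min and SD 15, 30, 45 or 60 min. PSG sleep efficiency S (TST divided by recording length) has mean 0.78 and SD 0.10 or 0.15. T and S are independent, and the windows coincide exactly.

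**Model.** PSG TST = T × S. Let CV_T = SD(T)/420, CV_S = SD(S)/0.78 and D = CV_T² + CV_S² + CV_T²·CV_S².

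- Device A calls a fixed share of every night sleep: r = CV_T / √D.
- Device B calls a random share, unrelated to S but with the same mean and spread: r = CV_T² / D, the square of A's value.

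Neither device carries any sleep/wake information.

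**One case in full.** For SD(T) = 30 and SD(S) = 0.10, CV_T = 30/420 = 0.0714 and CV_S = 0.10/0.78 = 0.1282. Then D = 0.00510 + 0.01644 + 0.00008 = 0.02162 and √D = 0.1470. Device A: 0.0714/0.1470 = 0.49. Device B: 0.00510/0.02162 = 0.24.

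| SD of recording length | A, SD(S) 0.10 | A, SD(S) 0.15 | B, SD(S) 0.10 | B, SD(S) 0.15 |
|---|---|---|---|---|
| 15 min | 0.27 | 0.18 | 0.07 | 0.03 |
| 30 min | 0.49 | 0.35 | 0.24 | 0.12 |
| 45 min | 0.64 | 0.48 | 0.41 | 0.24 |
| 60 min | 0.74 | 0.59 | 0.55 | 0.35 |

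Simulation agrees with these values to within about 0.01.

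**Sensitivity.** With mean 450 min, mean efficiency 0.80, SD(S) 0.08 to 0.20 and SD(T) 10 to 60 min, device A gives 0.09 to 0.80 and device B 0.01 to 0.64. If every night had the same length, B would give 0 and A's correlation would be undefined.

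**Does adjustment separate clock from device?** Take a weak device with the same mean and spread as PSG, whose sleep share correlates ρ = 0.30 with the PSG share. Its raw TST correlation is ρ + (1 − ρ) × (B's value). At the extremes of the table this is 0.30 + 0.70 × 0.033 = 0.32 and 0.30 + 0.70 × 0.549 = 0.68. The same weak device thus shows anything from 0.32 to 0.68 depending on how much nights vary. In simulation, the partial correlation given recording duration stayed near 0.30 (about 0.29 to 0.31) across all these settings.

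**The case against.** The strongest reply is that everything that fixes the size is assumed. The protocol gives no spread for recording length or efficiency. These are staff-run laboratory nights, and if their length is tightly standardised the effect is small. Device A is also the favourable case: having no error spread of its own, it shows the clock effect at its largest, whereas device B reaches only 0.03 to 0.07 at SD 15 min. Early sensor removal can break the shared window for some subjects. All of this stands, and it limits the claim to what could happen.

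A reader might infer that a device blind to sleep would certainly show a clearly positive and statistically significant TST correlation. The documents do not support that. They plan no test and set no alpha. Even against an assumed two-sided 5% level, the critical r at n = 100 is 0.197, which device A at SD 15 min with SD(S) 0.15 (0.18), and device B in several rows, would not be expected to reach.

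A reader might also infer that errors in REI go unexamined. They do not: Study analysis compares REI with AHI directly and assesses severity-category agreement, where large denominator errors could show.

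Finally, an adjusted correlation is still a correlation and does not reveal a constant over-call of sleep. Scoring the whole night as sleep when 78% is sleep lowers REI by 1 − 0.78 = 22% for the same event count, and neither added statistic is designed to show that. This is a fair limit on the remedy. So is the point that TST minutes, a comparison the objectives name, should not be dropped.

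**Conclusion.** The point holds in conditional form. The only planned TST analysis correlates minutes from a common recording window, so variation in night length could produce a positive correlation without good sleep/wake discrimination, and nothing planned would show how much of r arises that way. Under the main assumptions the clock contribution is about 0.18 to 0.74 for a fixed-share device and 0.03 to 0.55 for a random-share device. These ranges also rest on independence of recording length and efficiency; dependence between them would change the values.

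The issue is the interpretation of r for TST, not a decision rule, because the protocol has none. The unknown spread is itself a reason to report the benchmark: the study's own data would then show whether the effect is negligible or large.

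**What to change.** In Study analysis, keep the TST-minutes comparison and add beside it:

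- (a) the correlation between systems of sleep efficiency, defined as TST divided by the recording duration common to both. The partial correlation of the two TSTs given recording duration would also serve; it is closely related but not identical.
- (b) the clock-only benchmark: the correlation of PSG TST with recording duration in the same subjects.

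Base any statement that NightOwl detects sleep on (a), and read the raw TST correlation against (b). State how the common duration is defined when the sensor comes off early. Say in the text that (a) and (b) do not detect a constant over- or under-call of sleep.

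The cost is some analysis wording and a few lines of code. Recording durations should be obtainable from the PSG and NightOwl exports already listed in the dataset section, so no new data collection is needed. The downside is slightly more analysis and a likely lower quoted TST correlation.

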### Details of acquired dataset for each subject

Throughout the study, the following data will be collected for each included subject:

- Polysomnographic data (EDF format), by means of export from the sleep clinics' PSG software
- Respiratory events and sleep stages annotated by the sleep technician (EDF, TXT, or CSV format), by means of export from the sleep clinics' PSG software
- NightOwl sensor data, by means of export from the NightOwl database:
  - red and infrared PPG from finger (CSV)
  - accelerometry from finger (CSV)
- Subject's age, gender, weight, height, self-reported ethnicity, and self-reported race will be collected right before administering the PSG.

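### Does the unassigned external PSG score leave the reference for the main NightOwl analyses open?

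*Combined protocol and SAP*

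**What the plan says.** The Study analysis section of the combined protocol and SAP lists two main analyses. The first is the Pearson correlation of NightOwl's REI and TST with "the AHI and TST determined from the PSG". The second is agreement between NightOwl's severity categories and "those obtained by the manual analysis of the PSG".

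The next paragraph sends the coded PSGs to the company behind the MSSS, to establish "an external benchmark to which the NightOwl and PSG analysis could be compared". It cites a study in which that system, "complemented with manual editing, standardizes PSG scoring results within and across sleep centers". It concludes that using such a benchmark reduces "the impact of inter-scorer variability of current and future reports" on NightOwl's performance metrics.

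Two other sections bear on the reference. Under Scientific objectives, NightOwl's index is compared "to the AHI obtained from manual analysis of the polysomnography (PSG"), and for sleep time the text says "We will also compare the total sleep time (TST) derived by both systems". The list of data acquired for each subject includes "Respiratory events and sleep stages annotated by the sleep technician".

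**The concern.** Each PSG will carry two scores, one from the local technician and one from the external company. The plan gives the external score no statistic, no rank and no commitment to report. It does not say whether this study's benchmark will be the automatic or the edited score. The correlation analysis does not name a scorer.

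That seems to leave two unattractive readings. If local scoring is the reference, differences between scorers, and between the up to four centres that the patient code allows for, count as device error, and the benchmark does nothing about them in the main results. If the reference is open, it could be settled once both sets of results are known and the more favourable one presented as the main result. TST looks most exposed, because neither the objectives nor the correlation analysis says whose sleep staging supplies it.

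**Working it through.** **Which score is the reference?**

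| Quantity | Where the source is indicated | Reading |
|---|---|---|
| AHI | Scientific objectives: manual PSG analysis | Local manual scoring |
| Severity category | Study analysis, second main analysis: manual PSG analysis | Local manual scoring |
| TST | Acquired dataset: technician's sleep stages, the only staging listed | Local manual scoring, by inference |
| MSSS score | Study analysis, separate paragraph after the main analyses | Benchmark for both NightOwl and the PSG analysis |

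The last row matters. A benchmark to which the PSG analysis may itself be compared is distinct from the PSG analysis used as reference. The list of acquired data contains no MSSS output. Taken together, the sections give one coherent reading.

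**What would the choice of reference be worth?** The plan states no figure to reproduce, and it gives no scorer, centre or device error. What follows rests on assumed values, apart from n = 100.

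*Attenuation of a correlation.* Expected r = true r × √(reliability of the reference). With an assumed true r of 0.90:
- reliability 0.80: 0.90 × √0.80 = 0.805 (95% CI at n = 100: 0.723 to 0.865)
- reliability 0.95: 0.90 × √0.95 = 0.877 (0.823 to 0.916)

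If its errors are independent of the device's, a noisier reference therefore lowers NightOwl's apparent performance.

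*Category agreement by simulation.* Assumptions: 100 subjects in four centres of 25; median AHI 15; log-SD 0.8 or 1.0; device log-error SD 0.30; cut-offs 5, 15 and 30; 10,000 replicates. Local = truth + centre effect + scorer error; benchmark = truth + error. Cells show percent agreement with NightOwl at log-SD 0.8 / 1.0.

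| Local centre/scorer SD | Benchmark SD | Local | Benchmark | Better of the two |
|---|---|---|---|---|
| 0.10/0.10 | 0.10 | 73.3 / 76.0 | 74.5 / 77.0 | 75.5 / 78.0 |
| 0.10/0.10 | 0.14 | 73.3 / 75.9 | 73.2 / 75.9 | 74.9 / 77.5 |
| 0.20/0.15 | 0.25 | 68.9 / 71.9 | 68.9 / 71.9 | 71.2 / 74.1 |
| 0.20/0.15 | 0.10 | 68.9 / 72.0 | 74.5 / 77.0 | 74.8 / 77.3 |
| 0.30/0.20 | 0.10 | 63.8 / 67.2 | 74.5 / 77.1 | 74.6 / 77.2 |
| 0.10/0.10 | 0.20 | 73.2 / 75.9 | 71.1 / 73.9 | 74.2 / 76.8 |
| 0.10/0.10 | 0.30 | 73.3 / 75.9 | 66.6 / 69.8 | 73.5 / 76.1 |

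Differences from the table:
- Benchmark less noisy: it is ahead by 77.0 − 76.0 = 1.0 up to 74.5 − 63.8 = 10.7 points. The top value needs the largest assumed centre and scorer errors.
- Local less noisy: it is ahead by 75.9 − 73.9 = 2.0 up to 73.3 − 66.6 = 6.7 points.
- Equally noisy (second and third rows): the two differ by about 0. Taking the better one adds 74.9 − 73.3 = 1.6 up to 71.2 − 68.9 = 2.3 points over local scoring.

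For scale, the binomial standard error at n = 100 is √(0.759 × 0.241 / 100) = 4.3 points and √(0.689 × 0.311 / 100) = 4.6 points. Shared centre effects raise it to as much as 5.3 in the equal-noise cases.

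*TST.* Assumed true SD 70 min, device error SD 40 min, local centre/scorer SD 10/10 min and benchmark SD 14 min: r = 0.852 (local), 0.850 (benchmark) and 0.857 (better of the two). The gain is 0.857 − 0.852 = 0.005 to 0.857 − 0.850 = 0.007, against a sampling SD of about 0.028.

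**The case for a change.** The case for acting has substance. The variability sentence covers current as well as future reports and carries no qualifier, so a reader could take it to describe the two analyses listed just above it. The word manual could be stretched to an edited MSSS score. No sentence ties the technician's sleep stages to the TST comparison. If local scoring were much noisier than the benchmark, the choice of reference could move category agreement by up to 10.7 points under the assumptions above. The remedy would be a few sentences and a repeat of the same code, with no new data.

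Part of this stands: the benchmark comparison has no stated statistic or rank, the edited or automatic status is not declared, and the correlation analysis does not name its scorer. The rest is weaker. The editing phrase describes the cited study, and nothing attaches the external score to the category analysis. The variability sentence is conditional on using the benchmark, and holds for comparisons that do so. The 10.7 points come from assumed error sizes, and the direction reverses, by up to 6.7 points, when the benchmark is the noisier score. Above all, writing out the natural reading would keep local manual scoring as the reference and formalise a comparison the plan already envisages, so the main results would be the same.

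**Conclusion.** No change follows. This is missing detail that analysts would fill in the obvious way: technician scoring as the reference for AHI, severity category and TST, and the MSSS score as an additional comparison for both NightOwl and the local scoring. Someone following the plan on that reading obtains sound main results. Scorer and centre differences do remain in the pooled metrics, but that is what comparison with manual PSG scoring, the stated objective, entails. If those errors are independent of the device's, they work against NightOwl.

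The worry about choosing the reference afterwards is limited, because for AHI and severity category a switch to the external score would visibly depart from the stated reference. For TST the protection rests on inference. Under the assumed errors, picking the better of two equally noisy references is worth about 1.6 to 2.3 points of agreement and 0.005 to 0.007 in the TST correlation, both well inside sampling error at 100 subjects. Larger gaps need one score to be clearly noisier than the other, and the documents give no figure from which to judge that.

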#### Data Storage and Confidentiality

The data will be stored in a cloud storage system (Google drive with activated Google Vault) protected by password, which is only known by the Principal Investigator and Sponsor. Google Vault is SSAE 16, SOC 2 audited, and ISO 27001 certified and was specifically designed for users to meet legal data retention requirements

An audit trail of all changes made to data files can be reconstructed since each file addition and deletion is permanently logged. All data will be stored for at least 2 years after the completion of the study. All data belonging to the same subject will receive a unique patient code. This number will be composed of the center nr (1 to 4) followed by the enrolment nr of that subject (e.g. the third patient enrolled in center 1 will receive the nr 1-3).

For each center, a coding table will be maintained in paper format which maps the patient code to the patient's name. This coding table is securely stored and locked away when not in use and is temporarily maintained to allow for association between the NightOwl Sensor data (which is always coded such that the patient's name is never transferred to Ectosense NV) and PSG (which is coded upon upload to the cloud storage system). As soon as all PSG and data of all subjects has been exported, coded, and uploaded, the coding table will be permanently destroyed by means of secure shredding in order to render the dataset stored on the cloud storage system anonymous.

Only the anonymized data stored in the cloud storage system will be used for the analysis described above. Hence, none of the researchers performing the statistical analysis will have access to uncoded data.

